## 4.6.7 Povidone-Iodine Treatment

The povidone-iodine solution will contain 10% povidone-iodine (1% free iodine) in purified water as the only active ingredient. Products that list other inactive ingredients, including alcohol, will be permitted. The brand of the solution will be left to the discretion of the clinical site, although Methods Center personnel will confirm that the chosen solution is acceptable. Acceptable brands include, but are not limited to, Betadine® [Purdue Products, L.P. Stamford, CT] and Scrub Care® [Cardinal Health, Dublin, OH]. Clinical site personnel will store and handle the povidone-iodine solution as per the manufacturers' recommendations. Operating room personnel will apply the solution to the operative site as the final preoperative skin antisepsis preparation immediately prior to commencing surgical fixation. They will apply the solution as per manufacturer's directions for use (e.g., technique of application, duration of application, drying time, drying techniques, replacement of draping, etc.).

## 4.6.8 Chlorhexidine Gluconate Treatment

The CHG solution will contain 4% CHG in purified water as the only active ingredient. Products that list other inactive ingredients, including alcohol, will be permitted. The brand of the solution will be left to the discretion of the clinical site, although Methods Center personnel will confirm that the chosen solution is acceptable. Acceptable brands include, but are not limited to, Betasept® [Purdue Products, L.P. Stamford, CT] or Hibiclens® [Mölnlycke Health Care US LLC. Norcross, GA]. Clinical site personnel will store and handle the CHG solution as per the manufacturers' recommendations. Operating room personnel will apply the solution to the operative site as the final preoperative skin antisepsis preparation immediately prior to commencing surgical fixation. They will apply the solution as per manufacturer's directions (e.g., technique of application, duration of application, drying time, replacement of draping, etc.).

## 4.7 Perioperative Co-Interventions

To optimize the internal validity of the trial findings, key details of co-interventions known to influence the incidence of SSIs will be documented. Hospitals typically implement standard procedures to achieve quality process benchmarks designed to minimize SSIs. These benchmarks are outlined in several similar guidelines such as the Joint Commission's Surgical Care Improvement Project 10 Core Measures to prevent SSI, the Society for Healthcare Epidemiology of America compendium to prevent SSI, and prevention guides from the Institute for Healthcare Improvement and the Association of periOperative Registered Nurses. While these guidelines mandate core benchmark processes to minimize SSI, it is not practical or generalizable for the trial protocol to standardize the steps taken or co-interventions performed to achieve these core measures, since each participating hospital will already have their own implemented procedures. This is the primary rationale for the cluster-crossover design, in which each participating hospital will act as its own control for the effect of co-interventions. Therefore, four key approaches to account for and limit the potential differential application of co-interventions during the study periods will be performed: 1) study periods for each intervention are kept relatively short to improve the likelihood that newly implemented co-interventions will be equally distributed across both treatment solutions; 2) encourage participating hospitals not to make changes to their existing infection prevention interventions during the study periods; 3) document the co-interventions being used in the hospitals throughout the study periods; and 4) record any changes in cointerventions that do occur if mandated by a participating hospital's administration. To this end, a monitoring tool containing a list of commonly applied prophylactic co-interventions being used at the participating clinical sites will be completed every four months to document any changes to their infection prevention strategies during the study period.

## 4.8 Outcome Measures

#### 4.8.1 Primary Outcome

The primary outcome is SSI, guided by the CDC's National Healthcare Safety Network reporting criteria (2017), which includes superficial incisional SSI within 30 days and deep incisional or organ/space SSI within 90 days of fracture surgery (**Table 3**). Since the management of some open fractures may have more than one operative procedure as part of an intentionally staged surgical plan (e.g., multiple irrigation and debridements, wound closures, temporary stabilization surgeries, definitive fixation surgery), the primary outcome will include any SSI event from the date of open fracture to the end of the 30- and 90-day post-operative surveillance periods from their definitive

fracture management surgery. For participants with multiple open fracture regions, the date of the definitive fracture management surgery will be matched to the open fracture region with the SSI.

**Table 3: CDC Surgical Site Infection Criteria** 

	Surgical Site Infection Criteria					
Outcome	Description					
Superficial Incisional SSI	Date of event for infection occurs from the date of fracture to 30 days after the definitive fracture management surgery (where day 1 = the procedure date)  AND					
	involves only skin and subcutaneous tissue of the incision  AND					
	patient has at least one of the following:					
	a. purulent drainage from the superficial incision.					
	
 
b. organisms identified from an aseptically-obtained specimen from the superficial incision or subcutaneous tissue by a culture or non-culture based microbiologic testing method which is performed for purposes of clinical diagnosis or treatment (e.g., not Active Surveillance Culture/Testing [ASC/AST]).
 
c. superficial incision that is deliberately opened by a surgeon, attending physician or other designee and culture or non-culture based testing is not performed.
 
AND
 
					
	patient has at least one of the following signs or symptoms: pain or tenderness;					
	localized swelling; erythema; or heat.					
	
 
d. diagnosis of a superficial incisional SSI by the surgeon or attending physician or other designee.
 
					
	The following do not qualify as criteria for meeting the definition of superficial SSI:					
	
 
Diagnosis/treatment of cellulitis (redness/warmth/swelling), by itself, does not meet criterion "d" for superficial incisional SSI. Conversely, an incision that is draining or that has organisms identified by culture or non-culture based testing is not considered a cellulitis.
 
					
	
 
A stitch abscess alone (minimal inflammation and discharge confined to the points of suture penetration).
 
					
	
 
A localized stab wound or pin site infection- Such an infection might be considered either a skin (SKIN) or soft tissue (ST) infection, depending on its depth, but not an SSI Note: A laparoscopic trocar site for an operative procedure is not considered a stab wound.
 
An infected burn wound is classified as BURN and is not an SSI.
 
					
Deep	The date of event for infection occurs from the date of fracture to 90 days after the definitive					
Incisional SSI	fracture management surgery (where day 1 = the procedure date)  AND					
	involves deep soft tissues of the incision (e.g., fascial and muscle layers)  AND					
	patient has at least one of the following:					
	a. purulent drainage from the deep incision.					
	
 
a deep incision that spontaneously dehisces, or is deliberately opened or aspirated by a surgeon, attending physician or other designee, and organism is identified by a culture or non-culture based microbiologic testing method which is performed for purposes of clinical diagnosis or treatment (e.g., not Active Surveillance Culture/Testing [ASC/AST]) or culture or non-culture based microbiologic testing method is not performed
 
AND
 
					
	patient has at least one of the following signs or symptoms: fever (>38°C); localized					
	pain or tenderness. A culture or non-culture based test that has a negative finding does not meet this criterion.					
	c. an abscess or other evidence of infection involving the deep incision that is detected on gross anatomical or histopathologic exam, or imaging test					
Organ/Space	Date of event for infection occurs from the date of fracture to 90 days after the definitive fracture					
SSI	management surgery (where day $1 =$ the procedure date)					

Outcome	Description			
	AND infection involves any part of the body deeper than the fascial/muscle layers, that is opened or manipulated during the operative procedure AND			
	patient has at least one of the following:			
	
 
a. purulent drainage from a drain that is placed into the organ/space (e.g., closed suction drainage system, open drain, T-tube drain, CT guided drainage)
 
b. organisms are identified from an aseptically-obtained fluid or tissue in the organ/space by a culture or non-culture based microbiologic testing method which is performed for purposes of clinical diagnosis or treatment (e.g., not Active Surveillance Culture/Testing [ASC/AST]).
 
c. an abscess or other evidence of infection involving the organ/space that is
 
			
	detected on gross anatomical or histopathologic exam, or imaging test evidence suggestive of infection.			
	AND			
	meets at least one criterion for a specific organ/space infection site listed in Table 3 of the CDC			
	Procedure-associated Module (summarized in Table 4 below). 5 These criteria are found in the			
	Surveillance Definitions for Specific Types of Infections chapter. 			

\*The CDC criteria has been modified to include all definitive fracture management surgeries, as opposed to including only National Healthcare Safety Network procedures that require infection reporting.

The CDC criteria for classifying SSIs will be followed. If multiple tissue levels are involved in the infection, the type of SSI (superficial incisional, deep incisional, or organ/space) reported will reflect the deepest tissue layer involved in the infection during the surveillance period. The date of event will be the date that the patient met criteria for the deepest level of infection: 1) Report infection that involves the organ/space as an organ/space SSI, whether or not it also involves the superficial or deep incision sites and 2) Report infection that involves the superficial and deep incisional sites as a deep incisional SSI. The most relevant National Healthcare Safety Network Organ/Space SSI classifications are summarized in **Table 4**.

Table 4: Relevant Organ/Space SSI Sites

	BONE	Osteomyelitis
Organ/Space SSI	JNT	Joint or bursa infection
	РЛ	Prosthetic joint infection

All reported SSIs will be reviewed independently by an infection preventionist nurse and an orthopaedic surgeon who are members of the Adjudication Committee. Briefly, they will complete the review by examining all relevant information to determine if the SSI meets the CDC criteria of a superficial incisional SSI, deep incisional SSI, or organ/space SSI. The Committee will reach consensus on all reviewed SSIs. A hospital epidemiologist and infectious disease physician who are members of the Adjudication Committee will be available to provide guidance as needed. All members of the Adjudication Committee will be blinded to the treatment allocation.

## 4.8.2 Secondary Outcome

The secondary outcome is unplanned fracture-related reoperation within 12 months of the open fracture. This outcome has been used in previous open fracture trials and is defined as any unplanned surgery that occurred from the time of injury to 12 months post-injury that is associated with an infection at the operative site or contiguous to it, a wound-healing problem, or a fracture delayed union or nonunion. Common examples include any unplanned: 1) irrigation and

debridement of surgical incisions or open fracture wounds due to infections or wound healing problems; 2) revision wound closure for dehiscence; 3) soft tissue coverage procedure for infected or necrotic wound; 4) fracture delayed union or nonunion surgery (such as bone grafting or implant exchange); and 5) reoperation for hardware or prosthesis failure due to infection or bone-healing problems. Removal of hardware for soft tissue prominence or periprosthetic fracture are common examples of reoperations that will not be considered outcome events. Two orthopaedic surgeons who are members of the Adjudication Committee will independently review all reported unplanned fracture-related reoperations to determine if they meet the criteria for being a study event. The Committee will reach consensus on all reviewed unplanned fracture-related reoperations.

## 4.8.3 Exploratory Outcomes

Two exploratory definitions of infection will be used for sensitivity analyses of the primary comparison. The first exploratory outcome is fracture-related infection (FRI) within 12 months of the open fracture, defined by the confirmatory criteria for FRI outlined in a 2018 consensus definition. The FRI criteria has been selected as an exploratory outcome because the CDC criteria has been criticized for failing to adequately account for the complexities of infections in traumatic fractures. The FRI criteria attempts to improve upon the ability to detect infections specifically in fracture patients; however, this definition of FRI has not been fully validated or widely adopted.

The confirmatory criteria include the presence of one or more of the following signs/symptoms:

- 1) Fistula, sinus or wound breakdown (with communication to the bone or the implant).
- 2) Purulent drainage from the wound or presence of pus during surgery.
- 3) Phenotypically indistinguishable pathogens identified by culture from at least two separate deep tissue/implant (including sonication-fluid) specimens taken during an operative intervention. In case of tissue, multiple specimens (3) should be taken, each with clean instruments (not superficial or sinus tract swabs). In cases of joint effusion, arising in a joint adjacent to a fractured bone, fluid samples obtained by sterile puncture may be included as a single sample.
- 4) Presence of microorganisms in deep tissue taken during an operative intervention, as confirmed by histopathological examination using specific staining techniques for bacteria or fungi.

The second exploratory outcome is SSI using the CDC criteria within 12 months of the open fracture. This secondary outcome will use the same diagnostic CDC reporting criteria for the primary outcome (**Tables 3 and 4**); however, the timeframe for this outcome will be expanded to include all SSIs that occur within 12 months of open fracture. Similar to the rationale for using the FRI outcome, and the recommendations for a minimum of 12 months follow-up for orthopaedic fracture outcomes, this expanded timeframe will detect infections that occur beyond the standard CDC surveillance reporting periods. This modification of the CDC reporting periods has been used in previous orthopaedic fracture trials.

An infection preventionist nurse and an orthopaedic surgeon member of the Adjudication Committee will review all reported SSIs to determine if they meet the FRI confirmatory criteria and / or the CDC criteria following the processes described above (see Section 4.8.1).

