## 1.6 Why Iodophor Skin Preparations May Reduce Open Fracture Reoperations

While the primary rationale for using antiseptic skin preparation solutions is to reduce the risk of SSI, many fracture healing complications are associated with indolent infections. These low-grade infections typically do not exhibit clinical signs consistent with SSI. Instead, they present several months post-fracture fixation and are only detected from deep tissue samples collected during secondary surgeries to treat fractures that fail to heal (nonunion). Previous fracture non-union studies have identified an infectious etiology in 31–38% of cases.  Similarly, results from the FLOW trial suggest that 58% of the reoperation events were caused by fracture nonunion or a hardware failure related to infection, wound-healing problem, or bone-healing problem (n= 188/323). In addition, among a series of 211 patients requiring reoperation for deep post-operative fracture infections, 40% of open fracture infections occurred beyond the 90-day surveillance period for SSI.  Therefore, given the rationale that povidone-iodine may be more effective in

preventing SSI, it is clinically plausible that its use may also reduce unplanned open fracture reoperations.

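### Whether an infection found at nonunion surgery gets blinded FRI and 12-month SSI review depends on an unblinded site also reporting it as an SSI

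*Combined protocol and SAP*

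**What the plan says.** Section 4.8.3 defines two exploratory outcomes over 12 months from the open fracture: FRI by the confirmatory criteria, and SSI by the CDC criteria with a longer window. It sets the case source in one sentence: an infection preventionist nurse and an orthopaedic surgeon "will review all reported SSIs to determine if they meet the FRI confirmatory criteria" and/or the CDC criteria, following the process of Section 4.8.1. That process has the same starting point: "All reported SSIs will be reviewed independently by an infection preventionist nurse and an orthopaedic surgeon".

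Reoperations follow a different path. Section 4.8.2 lists surgery for delayed union or nonunion, including implant exchange, among its examples. It has two orthopaedic surgeons who "will independently review all reported unplanned fracture-related reoperations to determine if they meet the criteria for being a study event". No sentence passes a reoperation on to FRI or CDC review.

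Section 1.6 describes indolent infection as follows: "These low-grade infections typically do not exhibit clinical signs consistent with SSI". It adds that these infections appear several months after fixation and "are only detected from deep tissue samples collected during secondary surgeries to treat fractures that fail to heal (nonunion".

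Section 4.5 states that the orthopaedic team, including the study coordinators, cannot be blinded. Section 5.2.4, item 6, repeats the primary comparison with the two exploratory outcomes to see whether the conclusions depend on the definition of SSI.

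**The concern.** The purpose of an alternative outcome definition is to count cases that the main definition would miss, or to leave out cases that it would wrongly count. Here a case can meet the alternative definition only if a site has first reported it as an SSI. The infections that Section 1.6 describes do not look like SSI and surface at an operation, so their natural entry point is the reoperation stream, where the infection question is not asked. Two of the four FRI confirmatory criteria rest on operative specimens (concordant cultures from at least two deep specimens, and organisms on histology), which fits such cases closely.

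Two things are at stake. Sensitivity analysis 6 may undercount late infection. And the step that decides whether a culture-positive nonunion reaches blinded adjudication is a labelling decision by staff who know the allocation.

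**Working it through.** **Reading check.** Setting the sections side by side:

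- Entry to FRI and 12-month CDC review: a reported SSI (4.8.3, which follows 4.8.1).
- Entry to reoperation review: a reported unplanned reoperation. The question asked is whether it meets the reoperation definition (4.8.2).
- Link from the second stream to the first: none stated.
- Where low-grade infections are found: deep tissue at nonunion surgery (1.6), hence in the second stream.
- Who decides whether the case is also reported as an SSI: the site, which is not blinded (4.5).

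**Size of the gap.** The plan gives no figure for this, so what follows is an illustration built from the protocol's inputs:

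- N = 1,540; baseline SSI risk 12.5%; risk ratio 0.65; baseline reoperation risk 13%, with a similar effect size expected (5.1).
- Share of reoperations due to nonunion or hardware failure in the earlier open-fracture irrigation trial: 188/323 = 58.2%, which reproduces the stated 58% (1.6).
- Infectious cause among nonunions: earlier studies "identified an infectious etiology in 31–38% of cases" (1.6).

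Formula: cases at risk of being missed = N × mean reoperation risk × 188/323 × (0.31 to 0.38). Comparator: expected SSIs = N × mean SSI risk.

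*Scenario A, risk ratio 0.65 on both outcomes.*
- Reoperations: 1,540 × (0.13 + 0.0845)/2 = 165.2
- Nonunion or hardware failure: 165.2 × 188/323 = 96.1
- Infectious: 96.1 × 0.31 = 29.8 to 96.1 × 0.38 = 36.5
- SSIs: 1,540 × (0.125 + 0.08125)/2 = 158.8
- Share of combined total: 29.8/(158.8 + 29.8) = 15.8% to 36.5/(158.8 + 36.5) = 18.7%

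*Scenario B, no effect on either outcome.*
- Reoperations: 1,540 × 0.13 = 200.2
- Nonunion or hardware failure: 200.2 × 188/323 = 116.5
- Infectious: 116.5 × 0.31 = 36.1 to 116.5 × 0.38 = 44.3
- SSIs: 1,540 × 0.125 = 192.5
- Share: 36.1/(192.5 + 36.1) = 15.8% to 44.3/(192.5 + 44.3) = 18.7%

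The effect assumption has to be the same for both outcomes. Setting the no-effect count of 36 to 44 against the 159 SSIs of Scenario A would inflate the share. N cancels, so loss to follow-up spread evenly over both outcomes changes the counts but not the percentages.

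**Dependence on site reporting.** The documents do not say what fraction of such cases sites would report as SSIs. With none reported, the missed share is 16–19%. With half reported (an assumption), Scenario A gives 14.9/188.6 = 7.9% to 18.3/195.3 = 9.4%. With all reported, it is zero.

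**The case against.** The strongest reply is that the route is not closed. Table 2 has sites collect SSI data at every visit to 12 months. Section 4.8.4 has events identified at diagnosis and/or by clinical assessment and record review, with records obtained from other hospitals. Table 3 lets organisms from aseptically obtained deep tissue count towards the organ/space criteria, and Table 4 lists osteomyelitis. A site can therefore report a culture-positive nonunion as an SSI, and it will then be adjudicated. This stands. A reader might infer that indolent infections never reach infection review, but the documents do not support that. What they show is reliance on the site's label, with no rule behind it.

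A reader might also infer that the exploratory outcomes merely relabel the primary SSIs. They do not: the window runs to 12 months instead of 30 and 90 days after definitive surgery, and the FRI criteria differ. Nor would missing cases equally in both arms by itself force agreement with the primary result.

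Section 1.6 argues for the reoperation outcome, which counts unplanned nonunion surgery whether or not infection is recognised. Section 4.8.3 justifies its outcomes by criticism of the CDC criteria in fractures and by detection beyond the CDC windows, without naming indolent infection. Both points are fair, but infections found months later at nonunion surgery fall within that second purpose.

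Finally, Section 4.8.4 names culture results for SSIs and not for reoperations, which might suggest that they are not collected for the latter. The reoperation list is open-ended and the case report forms are not in the documents, so that cannot be concluded.

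**Conclusion.** The gap is real and limited. FRI and 12-month SSI are adjudicated only among site-reported SSIs, reoperations are reviewed for a different question, and nothing in the text joins the two. Blinded infection review of an infection found at nonunion surgery thus depends on an unblinded site also calling it an SSI, and sensitivity analysis 6 may under-ascertain late infection.

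The figure of 30 to 37 cases (Scenario A) or 36 to 44 (Scenario B), about 16–19% of the combined total, is an upper bound. It assumes that no such case is reported as an SSI, that the infectious share from nonunion studies applies to every nonunion or hardware-failure reoperation, and that no other late SSIs are reported. Each assumption pushes the share up, so the true share is lower. The second is doubtful because the 58% includes hardware failures related to infection, where the infection has already been recognised.

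The primary 30- and 90-day SSI result and the secondary reoperation result are not affected. The consequence is confined to exploratory outcomes within a set of sensitivity analyses that Section 5.2.4 says may be conducted.

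**What to change.** In Section 4.8.3, widen the set of cases reviewed from reported SSIs to reported SSIs plus all reported unplanned fracture-related reoperations. Use the same blinded process, with the infection preventionist nurse and an orthopaedic surgeon, whether or not the site reported an SSI. Make sure that operative culture and histology results, where taken in routine care, are available for that review.

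Cost: the nurse and a surgeon apply the FRI and CDC criteria to roughly 165 to 200 further cases at the protocol's assumed event rates, fewer where an SSI is already reported. This is more than an extra box on the reoperation form, because the reoperation review uses two surgeons and no nurse. It needs no new specimens, no new committee members, and no change to sample size or alpha. It cannot recover infections for which the operation left no recorded evidence. It is a cheap improvement.
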